### 5.6.1 Extent of Exposure

Extent of exposure will be summarized by categories of cumulative weeks as well as by categories of duration of exposure. The number and percent of subjects for each exposure category will be presented by treatment group. Duration of exposure is the number of days between the date the subject received the first dose of study drug and the date the subject received the last dose of study drug and will be summarized using descriptive statistics for

continuous variable by treatment group. Overall exposure (number of subject-weeks) is defined as summation over all subjects' exposure durations and will be summarized by treatment group, overall and by stratification factors.

### 5.6.2 Adverse Events

The AE verbatim descriptions (investigator terms from the CRF) will be classified into standardized medical terminology using the Medical Dictionary for Regulatory Activities (MedDRA). Adverse events will be coded to the MedDRA (Version 21.0 or higher) lower level term (LLT) closest to the verbatim term. The linked MedDRA preferred term (PT) and primary system organ class (SOC) will also be captured in the database.

A treatment-emergent AE (TEAE) is defined as an AE that emerged during treatment or within 28 days following the last dose of study drug, having been absent at pretreatment (Baseline) or

- Reemerged during treatment, having been present at pretreatment (Baseline) but stopped before treatment, or
- Worsened in severity during treatment relative to the pretreatment state, when the AE was continuous.

Only those AEs that are treatment emergent will be included in summary tables. All AEs, treatment emergent or otherwise, will be presented in subject data listings.

Treatment-emergent AEs (TEAEs) will be summarized by treatment group, overall and by stratification factors, on the Safety Analysis Set. The incidence of TEAEs will be reported as the number (percentage) of subjects with TEAEs by SOC and PT. A subject will be counted only once within a SOC and PT, even if the subject experienced more than one TEAE within a specific SOC and PT. The number (percentage) of subjects with TEAEs will also be summarized by maximum severity (mild, moderate, or severe). The number (percentage) of subjects with TEAEs will also be summarized by relationship to study drug (related and not related).

Summaries of common TEAEs will be produced.

TEAEs will be summarized by the following subgroups: on AChEI at baseline (Yes or Not), region (US, Europe, Japan), receiving memantine (yes or no), age (age < 65, 65 ≤ age < 80, age ≥ 80 years) and Hoehn & Yahr stage (0&I&II or III), receiving AChEI and/or memantine (none, AChEI only, memantine only, AChEI+memantine).

A subject data listing of all AEs leading to death will be provided.

The number (percentage) of subjects with treatment-emergent serious adverse events (SAEs) will be summarized by MedDRA SOC and PT for each treatment group, overall and by stratification factors. A subject data listing of all SAEs will be provided.

The number (percentage) of subjects with TEAEs leading to discontinuation from study drug will be summarized by MedDRA SOC and PT for each treatment group, overall and by stratification factors. A subject data listing of all AEs leading to discontinuation from study drug will be provided.

TEAEs associated with special situations such as overdose, misuse, abuse, medication error, pregnancy, TEAEs with signal of possible drug abuse potential, and those requiring additional Medical Monitor follow-up will be listed and summarized similarly.

A summary of non-treatment emergent AEs will be produced, these are adverse events which occurred >28 days after final dose of study drug.

### 5.6.3 Laboratory Values

Laboratory results will be summarized using Système International (SI) units, as appropriate. For all quantitative parameters listed in protocol Section 9.5.1.5 Safety Assessments (Laboratory Measurements), the actual value and the change from baseline to each post-baseline visit and to the end of treatment (defined as the last on-treatment value) will be summarized by visit, treatment group, overall and by stratification factors, using descriptive statistics. Qualitative parameters listed in protocol Section 9.5.1.5 will be summarized using frequencies (number and percentage of subjects), and changes from baseline to each post-baseline visit and to end of treatment will be reported using shift tables. Percentages will be based on the number of subjects with both non-missing baseline and relevant post-baseline results.

Laboratory test results will be assigned a low/normal/high (LNH) classification according to whether the value was below (L), within (N), or above (H) the laboratory parameter's reference range. Within treatment comparisons for each laboratory parameter will be based on 3-by-3 shift table that compares the baseline LNH classification to the LNH classification at each post-baseline visit and at the end of treatment. Similar shift tables will be used to compare the baseline LNH classification to the LNH classification for the highest and lowest value during the treatment period.

The Sponsor's Grading for Laboratory Values (see Appendix 13.1) presents the criteria that will be used to identify subjects with treatment-emergent markedly abnormal laboratory values (TEMAV). Except for phosphate, a laboratory value was determined to be a treatment-emergent markedly abnormal value (TEMAV) if the post-baseline grade increased from baseline and the post-baseline grade was greater than or equal to 2. For phosphate, a laboratory value was determined to be a treatment-emergent markedly abnormal value (TEMAV) if the post-baseline grade increased from baseline and the post-baseline grade was greater than or equal to 3. When displaying the incidence of TEMAVs, each subject will be counted once in the laboratory parameter high and in the laboratory parameter low categories, as applicable.

#### 5.6.4 Vital Signs

Descriptive statistics for vital signs parameters (diastolic and systolic blood pressure, pulse, respiration rate, temperature and weight) and changes from baseline for above parameters as well as orthostatic changes for diastolic and systolic blood pressure, pulse will be presented by visit and treatment group, overall and by stratification factors.

Orthostatic hypotension is defined based on the following criteria per protocol:

Drop in standing systolic blood pressure  $\geq 20$  mmHg compared to supine, or drop in standing diastolic blood pressure  $\geq 10$  mmHg compared to supine.

Treatment-emergent orthostatic hypotension means if at baseline subject did not have SBP drop  $\geq 20$  and no DBP drop  $\geq 10$  compared to supine, but developed one or more of these two events during postbaseline visits.

Orthostatic tachycardia by numerical criteria is defined by the following numerical criteria:

Standing HR increases by  $>30$  beats/min compared to supine AND absolute standing HR is  $>100$  beats/min.

Orthostatic tachycardia without orthostatic hypotension will be considered a true orthostatic tachycardia and an instance of treatment emergent true orthostatic tachycardia is defined below:

1. Orthostatic tachycardia by above numerical criteria
2. No orthostatic hypotension (i.e. neither standing SBP drop by  $>20$  nor standing DBP drop  $>10$  compared to supine) at the same time point.
3. Does not meet criteria #1 and #2 at Baseline.

Additionally, instances of orthostatic hypotension by numerical criteria and treatment-emergent orthostatic hypotension, and instances of orthostatic tachycardia by numerical criteria and treatment-emergent true orthostatic tachycardia will be summarized by treatment group and visit, overall and by stratification factors.

Listing of vital signs including orthostatic changes will be provided.

In addition, the number (percentage) of subjects with clinically notable vital signs will be summarized by treatment group. Table 6 presents the clinical notable ranges.

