7 INTRODUCTION

7.1 Indication

Lewy body dementias (LBD) are the second most common cause of dementia in subjects over 65 years of age. It comprises dementia with Lewy bodies (DLB) and Parkinson's disease dementia (PDD), which are considered to be different ends of the same spectrum. Both DLB and PDD share a common underlying pathology which involves deposition of cortical and subcortical Lewy bodies within neurons (comprising aggregates of alpha synuclein). Idiopathic Parkinson's disease is a progressive neurodegenerative disorder characterized by tremor, rigidity, bradykinesia, and postural instability, with onset typically in middle to late life. It is thought that up to 80% of patients with Parkinson's disease develop dementia some years after the onset of the motor features and they are classified as having PDD. In DLB, subjects develop dementia prior to or within 12 months ([McKeith, et al., 2017](#)) after the onset of the characteristic motor symptoms associated with Parkinson's disease ([Walker, et al., 2015](#)).

LBD (in the form of both DLB and PDD) involve similar profiles of cognitive dysfunction affecting attention, executive function, visuospatial domains and memory ([Aarsland, et al., 2003](#), [Walker, et al., 2015](#), [Biundo, et al., 2016](#)). Often, more than 1 aspect of cognition is impaired, interfering with the patient's daily, occupational or social functioning. While generally progressive, LBD are characterized by fluctuations in cognition and levels of consciousness, visual hallucinations, delusions, depression, anxiety, or other behavioral disturbances. Patients may also have autonomic impairment that may include urinary dysfunction and orthostatic hypotension, with susceptibility to falls early in the disease course.

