13. Other significant pathological findings on brain MRI at Screening, including but not limited to: any macrohemorrhage (greater than 10 mm at greatest diameter); an area of superficial siderosis; evidence of cerebral contusion, encephalomalacia, aneurysms, arteriovenous malformations, or infective lesions; evidence of multiple lacunar infarcts or stroke involving a major vascular territory, severe small vessel or white matter disease; space occupying lesions; or brain tumors (however, lesions diagnosed as meningiomas or arachnoid cysts and less than or equal to 1 cm at their greatest diameter need not be exclusionary)
14. Hypersensitivity to E2027 or any of the excipients.
15. A prolonged QTcF as demonstrated by triplicate ECG at the Screening or Baseline Visit (ie, mean value >450 msec).
16. Had symptomatic orthostatic hypotension or symptomatic orthostatic tachycardia which resulted in hospitalization or urgent medical review in hospital in the past 12 months before Screening.
17. Any other clinically significant abnormalities which in the opinion of the investigator, require further investigation or treatment or which may interfere with study procedures or safety in the following:
 - Physical examination, ECG, vital signs at Screening or Baseline Visit
 - Laboratory tests at Screening Visit
18. Malignant neoplasms within 3 years of Screening (except for basal or squamous cell carcinoma of the skin, or localized prostate cancer in male subjects). Subjects who had malignant neoplasms but who have had at least 3 years of documented uninterrupted remission before Screening need not be excluded.
19. Has a “yes” answer to C-SSRS suicidal ideation Type 4 or 5, or any suicidal behavior assessment within 6 months before Screening, at Screening, or at the Baseline Visit, or has been hospitalized or treated for suicidal behavior in the past 5 years before Screening.
20. Known or suspected history of drug or alcohol dependency or abuse within 2 years before Screening, current use of recreational drugs or a positive urine drug test at Screening. Subjects who test positive in the urine drug screen need not be excluded if in the opinion of the investigator, this is due to the subject taking prior/concomitant medications for a medical condition that is not exclusionary and not due to drug abuse.

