#### **5.1.2 Secondary Endpoints**

CGIC-DLB scale at 12 weeks of treatment

- Change from baseline at 12 weeks of treatment in the following endpoints:

- CFI score
- MMSE total score
- NPI total score, subscores and caregiver or informant distress score

Safety and tolerability of E2027 as measured by

- Incidence of adverse events including severe AEs, serious AEs, AEs resulting in discontinuation
- Incidence of orthostatic hypotension and orthostatic tachycardia
- Incidence of markedly abnormal laboratory values and shifts from baseline of laboratory values
- Incidence of abnormal ECG parameters and abnormal ECG findings
- Incidence of suicidality based on C-SSRS
- Changes from baseline in the total score of UPDRS-III

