## 5.6.6 Other Safety Analyses

### 5.6.6.1 C-SSRS

The C-SSRS responses will be mapped to C-CASA as suggested by the C-SSRS Columbia website [http://www.cssrs.columbia.edu/clinical\\_trials.html](http://www.cssrs.columbia.edu/clinical_trials.html).

Number (percentage) of subjects with any treatment-emergent suicidal ideation, suicidal behavior, and suicidality (suicidal ideation and/or behavior) will be displayed. “Treatment-emergence” is used for any new or worsened events during randomization phase (treatment and follow-up) compared with the baseline C-SSRS assessment. This will be produced for at any point during the study, and by visit.

Shift from baseline to the maximum suicidal ideation severity rating (0=no ideation present to 5=active ideation with specific plan and intent) during randomization phase will assess worsening of suicidal ideation. Any score greater than 0 indicates the presence of suicidal ideation while a score of 4 (active suicidal ideation with some intent to act, without specific plan) or 5 (active suicidal ideation with specific plan and intent) can be used to indicate serious suicidal ideation.

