## 8.2 Safety data handling

### 8.2.1 Baseline Safety

The baseline value for all safety endpoints will be the last non-missing measurement occurring prior to the first dose of the study medication.

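### SAP 5.6.4 reserves treatment-emergent orthostatic hypotension for subjects without it at one baseline reading, so no planned output counts, by arm, asymptomatic worsening of existing orthostatic hypotension

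*SAP*

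**What the plan says.** The secondary safety endpoints in SAP 5.1.2 (and protocol 9.7.1.1.2) include "Incidence of orthostatic hypotension and orthostatic tachycardia".

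SAP 5.6.4 calls a subject orthostatic hypotensive when the standing reading is lower than the supine one by at least 20 mmHg systolic or 10 mmHg diastolic. For the treatment-emergent category it says "Treatment-emergent orthostatic hypotension means if at baseline subject did not have SBP drop" at or above that cut-off (and no diastolic drop at or above its own), "but developed one or more of these two events during postbaseline visits". It gives no route by which worsening counts. Criterion 3 for treatment-emergent true orthostatic tachycardia has the same form.

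Baseline for every safety variable is "the last non-missing measurement occurring prior to the first dose of the study medication" (SAP 8.2.1). Protocol Table 6, note h, specifies single vital-sign measurements.

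Elsewhere the SAP does recognise worsening. A laboratory value is markedly abnormal "if the post-baseline grade increased from baseline and the post-baseline grade was greater than or equal to 2" (SAP 5.6.3; grade 3 for phosphate). For the C-SSRS, treatment emergence "is used for any new or worsened events during randomization phase" (SAP 5.6.6.1). SAP 5.6.2 includes continuous adverse events that became more severe on treatment.

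On who can enter, protocol 7.1 states: "Patients may also have autonomic impairment that may include urinary dysfunction and orthostatic hypotension". The exclusion aimed at this condition (criterion 16) removes a subject who "Had symptomatic orthostatic hypotension or symptomatic orthostatic tachycardia which resulted in hospitalization or urgent medical review in hospital" in the 12 months before Screening.

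**The concern.** The disease can itself bring orthostatic hypotension, and criterion 16 removes only cases that led to hospital care. Subjects who meet the numerical criteria at baseline can therefore be randomized. For them the treatment-emergent category is closed from the first dose, and one positive baseline reading is enough to close it.

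At stake is whether the report could show that E2027 deepens postural falls in subjects who already have them. Phase 1 does not answer this. Study 002 enrolled healthy subjects, and its treatment-emergent counts were also limited to orthostatic hypotension absent at baseline (protocol 7.1.1.2.2). The present trial measures supine and standing pressure after dosing at Weeks 2, 6, 9 and 12, so the readings needed will exist.

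**Working it through.** The plan states no rate, power or sample size for this endpoint, so there is no figure to reproduce. The check applies the rule as written and then traces one subject through each planned output.

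**Rule.** OH = systolic fall ≥20 or diastolic fall ≥10 mmHg. Treatment-emergent = (no OH at baseline) AND (OH at any later visit).

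| Baseline fall (SBP/DBP) | Later fall | OH after baseline? | Treatment-emergent? |
|---|---|---|---|
| 5/2 | 25/4 | yes | yes |
| 20/5 | 50/25 | yes | no |
| 22/5 | 22/15 (diastolic criterion newly met) | yes | no |
| 20/5 | 0/0, then 60/30 | yes | no |

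**What the other outputs show.** Take a subject whose systolic fall goes from 22 to 55 mmHg, without lightheadedness or intervention.

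- *All numerical instances by arm and visit (SAP 5.6.4):* counted, but a 22 mmHg and a 55 mmHg fall each add one.
- *Orthostatic-change statistics (SAP 5.6.4):* the extra 33 mmHg moves the mean of a 91-subject arm by 33/91 ≈ 0.4 mmHg. The 55 may appear as the arm's extreme value, because SAP section 5 reports minimum and maximum. No count of worsened subjects results.
- *Clinically notable values (SAP Table 6):* these are absolute limits, with systolic low below 90 and high above 160. A supine 150 with a standing 95 is a 55 mmHg fall and crosses neither limit.
- *Adverse events (protocol 9.5.1.5.5):* not reported, since there are no symptoms and no intervention.
- *Listing:* shows the readings, with no comparison between arms.

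**How many subjects the rule could remove.** Baseline prevalence p is an assumption, because the documents give none. With 91 randomized per arm (SAP section 4), the number who cannot count is 91 × p: about 9 at p = 10%, 27 at 30% and 46 at 50%.

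**Effect on a reported difference.** Suppose the drug adds a uniform 10 percentage points of new or worsened cases. The result depends on a denominator that SAP 5.6.4 does not state.

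| Assumed p | All-subject denominator: 10 × (1 − p) | Denominator of subjects without OH at baseline |
|---|---|---|
| 10% | 9 points | 10 points |
| 30% | 7 points | 10 points |
| 50% | 5 points | 10 points |

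Dilution by (1 − p) therefore appears only in the first case. Under either denominator, worsening among baseline-positive subjects adds nothing to the treatment-emergent count.

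**The case against.** The strongest reply is that the treatment-emergent count is not the endpoint. The endpoint is incidence of orthostatic hypotension, and SAP 5.6.4 tabulates every numerical instance by arm and visit whatever the baseline status. If orthostatic hypotension is intermittent (protocol 7.1.1.2.2 describes sporadic time points in Phase 1), a drug effect in baseline-positive subjects could raise visit-by-visit prevalence in the E2027 arm. Symptomatic cases, and those needing intervention, are adverse events, and the TEAE rule does count worsening. Syncope and falls also go to the Medical Monitor in detail (protocol 9.5.1.5.1). All of this stands. A reader might infer that subjects with baseline orthostatic hypotension vanish from the safety analysis, or that the secondary endpoint would miss a harm confined to them. The documents do not support either reading.

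Three further replies have partial force.

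- Exclusions 17 and 21 let the investigator turn away clinically significant vital-sign abnormalities or poorly controlled conditions. This may lower prevalence, but it rests on judgement and does not bar every subject who meets the numerical criteria.
- The comparator rules use grades or severity scales, whereas orthostatic hypotension here is yes or no. That explains the difference in form, but the fall is measured in mmHg and can be compared with baseline.
- Requiring absence at baseline keeps the concept used in Study 002. Consistency is a fair reason to keep a category of new cases. It is not a reason to leave worsening uncounted.

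**Conclusion.** The gap is real and narrow. Under SAP 5.6.4 a subject who meets either criterion at the single baseline reading cannot become treatment-emergent, and no other planned output counts, by arm, subjects whose existing asymptomatic orthostatic hypotension worsened. This conclusion rests on the wording of the rule and needs no assumption about prevalence.

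The size of the under-count cannot be computed. A reader might take the reduction of a 10-point excess to 9, 7 or 5 points as an estimate. It is not, because it needs both an assumed prevalence and an all-subject denominator that the SAP does not state. A reader might also picture a 20-point excess confined to a 30% baseline-positive subgroup, giving a true overall excess of 0.30 × 20 = 6 points against 0 in the treatment-emergent table. The arithmetic is sound, but nothing in the documents indicates that an effect would be confined in that way.

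No co-primary conclusion is affected. This is an avoidable blind spot in the descriptive reporting of a named safety endpoint, in a population where the protocol itself expects the condition.

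**What to change.** Before unblinding, amend SAP 5.6.4 to report, by arm and with each denominator stated:

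- new orthostatic hypotension among subjects without it at baseline;
- worsened orthostatic hypotension among subjects with it at baseline;
- new or worsened among all subjects.

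Add a shift table from the baseline fall to the worst post-baseline fall, in categories, for systolic and diastolic pressure separately. Make the matching change for true orthostatic tachycardia.

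The sponsor should prespecify the increment that counts as worsening, as an analysis category only. One example is a fall at least 20 mmHg systolic or 10 mmHg diastolic larger than the baseline fall. That borrows the size of the SAP's within-visit cut-offs; the SAP has no existing threshold for change between visits. No clinical rule changes.

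The cost is a short SAP edit and a few table rows from supine and standing readings already collected. Counts will be somewhat higher in both arms, partly because comparing one baseline reading with the worst of several later ones picks up measurement variability. The contrast between arms, rather than the level in either, is what should be read.

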9.5.1.5.5 VITAL SIGNS, HEIGHT AND WEIGHT MEASUREMENTS

Vital sign measurements (ie, SBP and DBP [mmHg] including orthostatic evaluations, pulse [beats per minute], respiratory rate [per minute], body temperature [in centigrade]), height (m), and weight (kg) will be obtained at the visits designated in the Schedule of Procedures/Assessments ([Table 6](#)) by a validated method. Blood pressure and pulse will be measured after the subject has been resting for 10 minutes in the supine position. Blood pressure and pulse will be measured again after standing up for 2 minutes. All BP measurements should be performed on the same arm, preferably by the same person. (revised per Amendment 01)

When vital signs are to be obtained concurrently with PK or other blood samples, the vital sign measurements will be performed prior to drawing blood samples in order to maximize the accuracy of blood sampling times while minimizing the potential effects of blood drawing on recordings obtained during safety assessments.

Orthostatic (postural) hypotension will be defined as either asymptomatic orthostatic hypotension (change in blood pressure upon standing without lightheadedness) or symptomatic orthostatic hypotension (change in blood pressure upon standing accompanied by lightheadedness).

Orthostatic hypotension will be recorded based on the following criteria:

- Drop in systolic BP ≥ 20 mmHg, or
Drop in diastolic BP ≥ 10 mmHg (revised per Amendment 01)

Occurrences of orthostatic hypotension as defined above that also meet any of the following criteria are considered clinically significant and will be reported as AEs in this study:

- Postural lightheadedness noted upon standing (ie, symptomatic orthostatic hypotension)
- Requires intervention (eg, resumption of recumbent position, IV fluids, etc.)

Postural lightheadedness upon standing if accompanied by orthostatic BP changes meeting the above criteria of orthostatic hypotension should be reported as AE of orthostatic hypotension. (revised per Amendment 01)

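### SAP 5.6.4 excludes hypotension from true orthostatic tachycardia with strict cut-offs (>20, >10) but defines hypotension with inclusive ones (≥20, ≥10), so a tachycardic reading exactly at a cut-off can be counted as both

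*SAP*

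**What the plan says.** SAP 5.1.2 lists "Incidence of orthostatic hypotension and orthostatic tachycardia" among the secondary safety measures. SAP 5.6.4 then sets the rules:

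- **Orthostatic hypotension**, stated to be per protocol. The systolic limb is "Drop in standing systolic blood pressure $\geq 20$ mmHg compared to supine". A diastolic fall of 10 mmHg or more qualifies as an alternative. The treatment-emergent version in the next paragraph repeats both inclusive limits.
- **Orthostatic tachycardia by numerical criteria**: "Standing HR increases by $>30$ beats/min compared to supine AND absolute standing HR is $>100$ beats/min".
- **True orthostatic tachycardia**, in concept: "Orthostatic tachycardia without orthostatic hypotension will be considered a true orthostatic tachycardia".
- **Treatment-emergent true orthostatic tachycardia**, in three criteria. The first is the numerical tachycardia rule. The second is "No orthostatic hypotension (i.e. neither standing SBP drop by $>20$ nor standing DBP drop $>10$ compared to supine) at the same time point". The third is "Does not meet criteria #1 and #2 at Baseline".

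Protocol 9.5.1.5.5, under "Orthostatic hypotension will be recorded based on the following criteria", gives the same inclusive limits as the SAP's hypotension definition: 20 mmHg or more systolic, or 10 mmHg or more diastolic.

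**The concern.** Criterion 2 presents itself as a restatement of the hypotension definition given a few lines earlier, but uses different inequality signs. The two versions disagree at a systolic drop of exactly 20 mmHg and a diastolic drop of exactly 10 mmHg. Blood pressure is recorded in whole numbers, so such drops are ordinary values.

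The purpose of true orthostatic tachycardia is to separate tachycardia alone from tachycardia accompanying a pressure fall. The two categories should therefore not overlap at a single time point. The protocol treats orthostatic effects as relevant here: section 7.1 names orthostatic hypotension as a feature of the disease, and section 7.2.2 lists postural orthostatic tachycardia among the events reported with E2027. At stake is a clean descriptive safety table, and the risk that two programmers code the same criterion differently.

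**Working it through.** **Rules as written.** Let S and D be the standing drops in systolic and diastolic pressure (mmHg).

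- Hypotension (SAP 5.6.4, protocol 9.5.1.5.5): S ≥ 20 or D ≥ 10.
- Criterion 2, literal: not (S > 20 or D > 10), that is, S ≤ 20 and D ≤ 10.
- Criterion 1: heart-rate rise > 30 and standing rate > 100 beats/min.

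**Where hypotension and criterion 2 both hold.** Either S = 20 with D ≤ 10, or D = 10 with S ≤ 20.

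**Enumeration.** Take whole-number drops with S from -20 to 60 and D from -20 to 40.

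- S = 20 with D from -20 to 10 gives 31 pairs.
- D = 10 with S from -20 to 20 gives 41 pairs.
- The pair 20/10 is in both lists, so the overlap is 31 + 41 - 1 = 71 pairs.
- No pair falls into neither category.
- With inclusive limits in criterion 2, the overlap is 0.

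**Example readings (S/D).**

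| Drops | HR rise | Standing HR | Hypotension | Criteria 1 and 2, literal | Criteria 1 and 2, inclusive limits |
|---|---|---|---|---|---|
| 20/5 | 35 | 110 | yes | yes | no |
| 15/10 | 35 | 110 | yes | yes | no |
| 20/10 | 35 | 110 | yes | yes | no |
| 20/12 | 35 | 110 | yes | no | no |
| 22/10 | 35 | 110 | yes | no | no |
| 20/5 | 10 | 80 | yes | no | no |
| 19/9 | 35 | 110 | no | yes | yes |

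Only the first three rows are double-classified. A threshold drop is not enough by itself: the heart-rate criteria must be met and the other pressure must not exceed its limit.

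**Criterion 3.** It applies criteria 1 and 2 at Baseline. A 20/5 Baseline reading with a heart-rate rise of 35 and a standing rate of 110 counts as Baseline true tachycardia, so a later episode is not treatment-emergent. This lowers the count, whereas a post-baseline threshold reading raises it. The net direction is not fixed.

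**Which tables can change.** SAP 5.6.4 tabulates four things: hypotension by numerical criteria, treatment-emergent hypotension, tachycardia by numerical criteria, and treatment-emergent true tachycardia. The first three do not use criterion 2. Only the fourth does.

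**Size.** The documents give no distribution of standing pressure changes and no per-reading tachycardia rate for this population. For illustration only, assume:

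- mean systolic drops of 3 to 8 mmHg (SD 12 to 16);
- mean diastolic drops of 0 to 2 mmHg (SD 8 to 9), independent of systolic;
- 1% to 5% of readings meeting the heart-rate criteria, independent of pressure.

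The share of readings in the overlap region is then 3.2% to 4.2% if recorded to 1 mmHg and 6.4% to 8.5% if recorded to even numbers. Multiplying by the heart-rate share gives 0.032 × 0.01 = 0.03% up to 0.085 × 0.05 = 0.4% of readings. With 182 subjects that is about 0.06 to 0.8 subjects per visit.

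**The case against.** The strongest reply is that the governing words of criterion 2 are the absence of orthostatic hypotension, a term already defined in the same section and in the protocol. A programmer who uses the defined term gets no overlap, and the strict signs are then a drafting slip. No program is in the documents (SAP section 9 places derivation rules elsewhere), so no double count has been shown to occur. That stands: the defect is in the text as literally written. It does not remove the need to correct it, because the explicit numbers can just as reasonably be coded. Nor is a text-extraction fault likely, since the inclusive sign survives elsewhere in the same section.

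Three stronger readings are tempting, and the documents do not support them.

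- A reader might infer that every exact-threshold reading is counted twice. Criterion 1 and the limit on the other pressure rule that out.
- A reader might infer that the incidence of hypotension is affected. Its definitions are consistently inclusive and do not refer to criterion 2.
- A reader might take the share of readings at a pressure threshold as the size of the error. That share ignores the heart-rate criteria and rests on assumed distributions.

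Exclusivity is also intended only within a time point. A subject may properly have hypotension at one visit and true tachycardia at another.

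**Conclusion.** The point holds in limited form. SAP 5.6.4 contradicts itself at exactly 20 mmHg systolic and 10 mmHg diastolic. As literally written, it lets a tachycardic reading at a threshold be both hypotension and tachycardia without hypotension, and lets such a reading at Baseline suppress a later treatment-emergent count.

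The reach is one descriptive tabulation within a secondary safety endpoint. Efficacy, type I error and sample size are untouched. The logical overlap needs no assumption beyond a literal reading. Its frequency does depend on assumptions: the illustrative range of under one subject per visit takes heart rate and pressure change as independent, and a correlation between them could raise it. The only tachycardia rates in the documents (protocol Table 3: 7 of 30 on E2027, 3 of 10 on non-Japanese placebo) are for any time during a 14-day treatment period in healthy subjects and cannot be converted to a per-reading rate. This is a minor correction worth making.

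**What to change.** In SAP 5.6.4, replace the parenthesis in criterion 2 by the complement of the SAP's own definition: neither a standing systolic drop of at least 20 mmHg nor a standing diastolic drop of at least 10 mmHg compared to supine. Criterion 3 refers back to criterion 2, so it is corrected at the same time. Check that the derivation code for post-baseline and Baseline readings uses the same signs, ideally by computing one hypotension flag and reusing it.

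The change introduces no new clinical threshold, collects no new data and alters no other analysis.
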